### Study design

General points:

Although the CTS is currently available (Clip-Tone on prescription and Clip-Tone Buddy app available to purchase on App store) we currently do not know how effective it is in improving and maintaining inhaler technique in patients with asthma. If this data were available, health care professionals would know whether to advise patients to use it. Potentially this is a low-cost solution to a large problem within the asthma community.

In order to gain this evidence, it is important to compare the use of the CTS with "usual care". Some patients will already have good inhaler technique and have adequate education on how to use their inhaler – we do not want to interfere with this and so all patients in the study will continue to see their HCPs as and when they are invited to do so or if the need arises during the study. We will simply ask patients to report what input they have had when we follow them up at each visit. We plan to randomly assign half the participants to the CTS, along with their "usual care" and half to continue with their "usual care" only.

During the Covid pandemic patients have become accustomed to having many of their health consultations performed remotely by video or telephone consultation. The public in general have become used to talking with friends, family, colleagues and having work meetings via Zoom, Microsoft Teams or Facetime. Virtual consultations generally are time saving with no travel time

for participants and easier to fit into our everyday lives. Participants who enter into this study need to have the availability of a mobile smartphone or a tablet in order that they can participate. For these reasons we have planned to carry out the study using virtual consultations. We appreciate that the nature of the study will exclude some members of the public but with smartphone ownership at >90% of all UK under 65-year-olds (OFCOM data 2020) the numbers excluded in this study will be small.

We will reassess recruitment within the first 4-8 weeks of the study and if it is felt participants are being excluded because they want to have face-to-face consultations rather than virtual ones, we will source rooms to see participants and submit an amendment to the protocol and ethics committee.

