# **10 STATISTICAL CONSIDERATIONS**

## **10.1** Statistical Analysis

Intention to treat analysis will assess between-group differences in the patient improvement (relative to baseline) in inhaler technique score and inhalation time (at 6 month follow-up). Assessment of in inhaler technique will be done for each visit (1-, 3- and 6-month follow-ups) using parametric and non-parametric tests of differences in distribution location (mean for parametric tests, median for non-parametric tests).

Similar analysis will be performed on a secondary outcome measures – asthma control score (obtained from the ACQ).

More complex analysis, e.g., mixed-effects (multi-level) models, to study the temporal evolution of the primary and secondary outcomes will only be performed if is deemed warranted by the results of the initial between-group analysis.

The proportion of patients in each group at each visit with a correct inhaler technique (achieving maximum score of 10) will be compared within groups over each visit. Comparisons will be made within groups and between groups, using appropriate tests of the follow-up specific 2x2 contingency tables.

We will seek to examine any correlation between frequency of use of the Clip-Tone system in the intervention group to mean inhaler technique scores. Identification of most frequent errors in each group will also be explored (i.e., does CTS have an impact on particular steps?).

We will also intend to carry out per-protocol analysis which will include those participants in the intervention group who used the Clip-Tone Buddy at least once per week in the first month and at least once per fortnight in thereafter. Appropriate parametric and non-parametric tests will be used.

Descriptives of frequency of CTS use and change of use over time will also be carried out. Characteristics of participants who had higher compliance will also examined to identify if the Clip-Tone Buddy app had particular suitability for particular groups of people.

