## 10.2 Sample Size

To calculate the sample size, we identified previous studies examining interventions to improve inhaler technique. To appropriately power the study to understand if the intervention has a significant impact on improving inhaler technique, or if any improvement observed is as a result of chance (i.e., no significant difference between the intervention and care as usual groups) we will recruit 126 participants. The sample size calculation has been carried out using data from a previous study [20]. In this study, participants had a mean baseline score of 6.8 in both the intervention and control groups. At the end of the study participants in the control group had a mean score of 8.9 (s.d. 1) and the intervention group had a score of 9.5 (s.d. 1). Assuming that the intervention studied here will have a similar impact we calculate a minimum sample size of 88 will be required to power the study to a 0.05 significance level. Recruitment of 126 patients will allow the study to still be adequately powered with up to a 30% drop-out rate. The power calculation takes account of the likelihood that participants in the care as usual group will also be likely to show some improvement in technique.

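### The first-listed 6-month comparison is improvement from baseline on a score capped at 10, while the sample size is for final scores; adjusting the 6-month score for baseline is a free gain

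*Protocol*

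**What the plan says.** Protocol section 10.1 opens with an intention-to-treat comparison at 6 months of "between-group differences in the patient improvement (relative to baseline) in inhaler technique score". Technique at each visit is to be examined with parametric tests of means and non-parametric tests of medians. No baseline covariate is mentioned. The same section gives the top of the scale ("achieving maximum score of 10") and plans 2x2 comparisons, within and between groups, of the proportion reaching it at each visit.

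Section 10.2 takes its figures from a previous study: "mean baseline score of 6.8 in both the intervention and control groups", then at the end "control group had a mean score of 8.9 (s.d. 1) and the intervention group had a score of 9.5 (s.d. 1"). It adopts them for this trial ("Assuming that the intervention studied here will have a similar impact") and arrives at 88 participants, raised to 126 for 30% dropout.

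Section 5.2 (Study design) acknowledges that "Some patients will already have good inhaler technique and have adequate education on how to use their inhaler", and the inclusion criteria in 6.1 set no upper limit on baseline technique. The Methods summary in section 2 describes the sample size differently, as detecting a 30% difference in a proportion.

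**The concern.** The expected CTS mean lies half an SD below the top of the scale. For anyone who scores 10 at 6 months, improvement is 10 minus the baseline score. Among those participants it varies only with where they started, and someone already at 10 cannot improve at all.

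The comparison listed first is also not the one the trial was sized for. The 88 rests on the SD of the final score. The SD of improvement depends on the baseline SD and the baseline-to-final correlation, and the protocol gives neither. If the SD of improvement is well above 1, the trial has less than its designed power for that comparison. The baseline score that would recover this is already being collected.

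**Working it through.** **1. The plan's own figure.** Difference 9.5 − 8.9 = 0.6, SD 1, two-sided 5%. Power and sidedness are not stated; 80% two-sided is what reproduces the figure.

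n per arm = 2 × (1.96 + 0.842)² × 1² / 0.6² = 43.6, so 44 per arm and 88 in total. 88 / 0.70 = 125.7, so 126. Both stated numbers reproduce, for a comparison of final scores with SD 1.

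**2. What change needs to match this.** With final SD 1, baseline SD s and correlation r:

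SD of change = √(s² + 1 − 2rs)

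This is at most 1 only if r ≥ s/2. The correlation would have to reach 0.5 at s = 1, 0.75 at s = 1.5 and 1.0 at s = 2.

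**3. Power of change with no ceiling.** Power ≈ Φ(0.6 / (SD of change × √(2/44)) − 1.96):

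| s | r | SD of change | Power |
|---|---|---|---|
| 1 | 0.3 | 1.18 | 66% |
| 1 | 0.5 | 1.00 | 80% |
| 1.5 | 0.3 | 1.53 | 45% |
| 1.5 | 0.5 | 1.32 | 57% |
| 2 | 0.3 | 1.95 | 30% |
| 2 | 0.5 | 1.73 | 37% |

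So a large loss appears before any cap is imposed.

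**4. How full the top category is.** Assume whole-point scores from 0 to 10. Let d = 10 − score. Mean 9.5 and SD 1 require E(d) = 0.5 and E(d²) = 1 + 0.25 = 1.25.

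- Smallest share at 10: 57.5% at 10, 41.67% at 9, 0.83% at 0. Check: E(d) = 0.4167 + 0.0833 = 0.5; E(d²) = 0.4167 + 0.8333 = 1.25.
- Largest share at 10: 79.17% at 10, 12.5% at 8, 8.33% at 7. Check: E(d) = 0.25 + 0.25 = 0.5; E(d²) = 0.5 + 0.75 = 1.25.

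Within rounding of the published figures the minimum falls: 53.9% (mean 9.5, SD 0.8), 52.5% (9.45, SD 1), 46.1% (9.45, SD 0.6). With half-point scoring it is 20%, and with tenth-point scoring 0%. In the usual-care arm (8.9, SD 1, whole points) the share at 10 can be anywhere from 1% to 45%.

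**5. Power with the ceiling.** Simulation at 44 per arm, whole-point maximum-entropy scores matched to baseline mean 6.8 and to 8.9 v 9.5 (SD 1). Baseline SD and the latent correlation (before conversion to whole points) are assumed. 8,000 replicates per row:

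| Baseline SD | Latent correlation | t-test on change | 6-month score adjusted for baseline |
|---|---|---|---|
| 1 | 0.3 | 63% | 80% |
| 1 | 0.5 | 72% | 84% |
| 1 | 0.7 | 82% | 89% |
| 1.5 | 0.3 | 42% | 80% |
| 1.5 | 0.5 | 50% | 83% |
| 1.5 | 0.7 | 61% | 90% |
| 2 | 0.3 | 28% | 80% |
| 2 | 0.5 | 33% | 84% |
| 2 | 0.7 | 40% | 90% |

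A separate simulation on the same kind of assumptions gave 31–86% for change (31–46% at baseline SD 1.5–2 and correlation 0.3–0.5) and 78–91% for the adjusted score. The two agree to within a few points.

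The ceiling weakens the observed correlation: a latent 0.3 becomes about 0.22 in the CTS arm, and 0.7 becomes about 0.50 to 0.54. With 63 per arm and no dropout, the t-test on change reaches 68–89%, 46–71% and 34–49% at baseline SD 1, 1.5 and 2 (latent correlation 0 to 0.6).

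**6. What the ceiling does not do.** A t-test on the capped 6-month score keeps about 78% power in these runs, close to the designed 80%. Type I error on the capped scores stays near 5% (4.5–5.0% for the t-test, 4.4–5.4% for the rank test). The planned comparison of the proportion scoring 10 has about 94% power for these shapes (69% v 32%), falling to 66% if the CTS arm sits at its 57.5% minimum.

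**The case against.** A reader might infer that saturation itself ruins the main comparison or makes it invalid. The documents do not support that. Steps 3 and 5 show a similar loss with and without a cap. If the earlier study's scale also ended at 10, the expected 0.6 is a difference in observed scores and already contains the ceiling.

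A reader might also take it as settled that at least 57% of the CTS arm will score 10, or that its median must be 10. Both need whole-point scoring and an earlier scale ending at 10. A checklist of steps makes whole points plausible, but the protocol does not say so.

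The plan is not blind to saturation either. Section 10.1 already compares the proportion scoring 10 between groups. Since section 2 describes the sample size as a difference in a proportion, which analysis is the main one is not fully settled.

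Finally, the loss rests on a baseline SD and correlation that the protocol does not give. At baseline SD 1 and latent correlation 0.7, change has about the designed power. All of this stands. It narrows the point but does not remove it: the improvement comparison is written into the protocol, it is not the quantity used for the sample size, and in every setting simulated the baseline-adjusted score did better.

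**Conclusion.** The point holds as a free improvement, not as a flaw that invalidates the trial. The first-listed comparison uses change, while 88 participants give 80% power for final scores with SD 1. At 44 per arm, power on change is roughly 30% to 85% over baseline SD 1 to 2 and latent correlation 0.3 to 0.7, and roughly 30% to 50% at baseline SD 1.5 to 2 with correlation 0.3 to 0.5. The baseline-adjusted 6-month score gives roughly 78% to 91%.

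These figures assume whole-point scores, maximum-entropy shapes and the section 10.2 means and SDs on this trial's scale. Most of the loss comes from using change. The ceiling adds to it by loosening the link between baseline and final score.

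**What to change.** In section 10.1, replace the unadjusted tests of improvement as the main 6-month comparison with the between-group difference in the 6-month technique score, by intention to treat, with baseline score as covariate.

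Because of the ceiling, add a proportional-odds model of the 6-month score with baseline as covariate, sparse low scores pooled, as a sensitivity analysis. It reached 96–100% power in simulation, but that gain depends on the assumed score shapes and statisticians can reasonably differ on making an odds ratio primary. Keep the planned comparison of the proportion scoring 10, and report the share at 10 at baseline by arm.

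The cost is wording and slightly more analysis work. No new data or participants are needed, and the result stays a mean difference in points.

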## **Methods**

[figure not shown]
This study involves a randomised controlled trial of the use of the CTS versus usual care in patients with asthma who are using pMDI devices. Participants will be primary care patients aged 16 years and over who are prescribed regular pMDI medication for asthma. After standard inhaler technique and asthma assessment, each of the participants will be randomised to either receive care as usual or to receive the CTS. All patients will be followed up remotely at 1 month, 3 months and 6 months following enrolment. At each follow-up, inhaler technique will be assessed and scored using the validated UK inhaler group checklist, asthma control questionnaire (ACQ5) completed and any relevant unscheduled GP or hospital visits recorded. To show a difference of 30% in the proportion of participants (63 per group), will be recruited allowing for a 20% dropout rate. Secondary objectives of this study are dedicated towards developing understanding of how patients perceive use of Clip-Tone System in a real-world setting. A health economic assessment of the data will also take place.

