#### Exclusion criteria:

1) Using a spacer to assist with using their inhaler.

- 2) Prescribed oral steroids for asthma in the preceding 1-month
- 3) Medication is not self-administered
- 4) Treatment for acute asthma in an ICU within the previous 3 years
- 5) Insufficient understanding of spoken and/or written English (as judged by the researcher).

Potential recruits will attend a baseline visit where formal content to participate will be taken and eligibility criteria checked. Initial inhaler technique will be assessed using a formal inhaler technique score. Asthma control questionnaire will be completed (a validated asthma questionnaire to detect level of asthma symptom control). Some baseline questions will be asked about their asthma e.g. medication, exacerbations, HCP involved. We plan to randomise 126 participants, half to CTS and half to Usual care.

Those allocated to the CTS group will have the Clip-Tone posted to them along with a voucher code for the Clip-Tone Buddy App and a short virtual visit will be arranged the following week to ensure the participant knows how to use the device and the features of the app.

Participants will all attend 3 further follow-up visits in 1, 3 and 6 months. For the "usual care" group these visit dates will be calculated from the baseline appointment, and for the CTS group these will be calculated from the training visit. The difference in these calculations is to allow for any delay in the participant commencing use of the CTS, to ensure that 6 months of active intervention usage are accurately recorded.

At each follow up visit inhaler technique will be assessed using the formal inhaler technique score. Asthma control questionnaire will be completed and a few questions will be asked about asthma health care utilisation since the previous visit. Those in the CTS group will be asked to send a screen shot of the app use and to give some feedback on useability, frequency of use, barriers to use and suggested improvements.

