# 5.3 End of study

A participant is considered to have completed the study if they have completed the baseline assessment, the intervention guidance appointment (if randomised to the intervention group) and the follow up appointments at 1, 3 and 6 months. As a minimum at the baseline and all follow up appointments, inhaler technique assessment and ACQs will be completed. Participants may opt out of the video recording of inhaler use if desired (these blinded assessments are intended to verify the veracity of the researcher assessment who cannot be blinded due to the nature of the intervention).

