## 6.4 Randomisation:

Once consent has been obtained and baseline data has been gathered, participants will then undergo simple randomisation. Approximately 50% of people will be allocated to each group. Allocation into the study group will be carried out by the dedicated researcher. Prior to the recruitment of the first patient a random sequence of 150 (greater than the number that will ultimately be recruited) will be generated using the website random.org/sequence. Each participant will be allocated the next available number of the randomly generated sequence. If this is an even number the participant will be allocated to care as usual group and if this is an odd number they will be allocated to the intervention group. For those allocated to the intervention group, a Clip-Tone device along with instructions how to download the app will be sent to them by post and a training appointment will be made. Because of the nature of the intervention, it is not possible to blind participants to which group they are allocated to.

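### The between-arm test of the proportion with correct technique cannot use the baseline technique score; adjusting for it would give an optional, low-cost gain in precision on this endpoint only

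*Protocol*

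**What the plan says.** Section 10.1 sets out two analyses of inhaler technique.

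- **Score.** The leading analysis assesses "between-group differences in the patient improvement (relative to baseline) in inhaler technique score", so baseline enters through the change score.
- **Proportion.** Later in the same section, the share of participants "with a correct inhaler technique (achieving maximum score of 10") is compared within and between groups "using appropriate tests of the follow-up specific 2x2 contingency tables". No stratified or regression version is named. Only the choice among 2x2 tests is left open.

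Models that could carry a covariate are conditional: mixed-effects models "will only be performed if is deemed warranted by the results of the initial between-group analysis".

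The baseline score is available for everyone. Section 5.2 says of the baseline visit: "Initial inhaler technique will be assessed using a formal inhaler technique score". Section 5.3 makes it a minimum item: "As a minimum at the baseline and all follow up appointments, inhaler technique assessment and ACQs will be completed". Section 6.4 places randomisation after baseline data collection, and "participants will then undergo simple randomisation".

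The Methods summary in Section 2 links the group size to a proportion: "To show a difference of 30% in the proportion of participants (63 per group"), with a 20% dropout allowance. Section 10.2 instead derives 88, raised to 126 for 30% dropout, from mean scores of 8.9 and 9.5 with SD 1.

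**The concern.** The proportion with fully correct technique is a direct reading of the primary question in Section 4.1, which asks about achieving and maintaining effective technique. It also appears to be the quantity behind the 30% in the Methods summary. Section 5.2 accepts that some patients will already have good technique on entry. In a single-visit 2x2 table, a participant who started at 10 and stayed there counts the same as one who rose from a low score. If baseline score predicts who is correct at follow-up, part of the outcome variation is explainable from data already in hand, and the planned test leaves it in the error. The plan uses baseline for the score and drops it for the proportion. What is at stake is some power, and a wider confidence interval than necessary, on this endpoint.

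**Working it through.** **1. The plan's own figure.** For means, n per arm = 2(z₀.₉₇₅ + z₀.₈₀)² × SD² / difference² = 2 × (1.960 + 0.842)² × 1² / 0.6² = 2 × 7.85 / 0.36 = 43.6, so 44 per arm and 88 in total. Then 88 / 0.70 = 125.7, so 126. Section 10.2 is reproduced if power is 80% and the test two-sided, neither of which it states. The binary endpoint plays no part in this figure.

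**2. Evaluable numbers.** 63 × 0.80 = 50.4, about 50 per arm (Methods summary). 63 × 0.70 = 44.1, about 44 per arm (Section 10.2). No dropout: 63 per arm.

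**3. Inputs the protocol does not give (assumptions).** These are the two response rates, the baseline SD, and the correlation rho between baseline and the underlying follow-up score. A 30-point gap was placed at several levels, and rho was set at 0.3, 0.5 and 0.6 to 0.7. Where baseline was made an integer score capped at 10, its mean was 6.8 (from the study cited in Section 10.2) and its SD an assumed 1.5.

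**4. Unadjusted power for a 30-point difference (normal formula, two-sided 5%).**

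| Rates | 44 per arm | 50 per arm | 63 per arm |
|---|---|---|---|
| 10% vs 40% | 91.5% | 94.6% | 98.0% |
| 20% vs 50% | 85.2% | 89.4% | 95.1% |
| 35% vs 65% | 81.5% | 86.2% | 93.0% |

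**5. Simulated gain at rho 0.5.** Baseline and underlying follow-up were bivariate normal, with follow-up cut to give the stated rates. Pearson chi-square was compared with the test for arm in a logistic model that includes baseline. Gains were computed before rounding.

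| Per arm | Rates | Chi-square | Adjusted | Gain (points) |
|---|---|---|---|---|
| 50 | 20% vs 50% | 89.6% | 93.8% | 4.1 |
| 50 | 30% vs 60% | 87.3% | 91.4% | 4.1 |
| 50 | 35% vs 65% | 87.5% | 91.2% | 3.7 |
| 50 | 10% vs 40% | near 95% | | about 2 |
| 44 | 20% vs 50% | | | 3.3 |
| 44 | 30% vs 60% | | | 7.1 |
| 44 | 35% vs 65% | 80.8% | 88.4% | 7.6 |
| 63 | 20% vs 50% | 95.8% | 97.8% | 2.0 |
| 63 | 35% vs 65% | 93.9% | 96.3% | 2.4 |

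With no treatment effect (50 per arm, 30% in both arms) both tests rejected in 5.2% of runs, so both hold their level.

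**6. Other correlations, 50 per arm.** At rho 0.3 the gains for the first three rows were 1.7, 1.3 and 0.5. At rho 0.625 they were 6.0, 6.9 and 7.0. At rho 0.7 the range over the 30-point scenarios is about 3 to 8.

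**7. Formula cross-check.** Adjustment multiplies the variance by about 1 − r², where r is the correlation of baseline with the yes/no outcome. At rho 0.5, r was about 0.38 for 35% vs 65%. From 86.2%: (1.089 + 1.960) / √(1 − 0.378²) − 1.960 = 3.049 / 0.926 − 1.960 = 1.33, which is 90.9%, a gain of 4.7 points against 3.7 simulated. At 44 per arm, from 81.5%: 2.856 / 0.926 − 1.960 = 1.13, which is 87.0%, a gain of 5.5 against 7.6. The top figure at 44 per arm therefore owes something to the discreteness of the chi-square test.

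**8. Rates implied by the Section 10.2 means.** Cutting normal curves at 9.5 gives P(Z > 0.6) = 27% and P(Z > 0) = 50%. Power at 50 per arm and rho 0.5 rises from 65.3% to 72.6%, and the gain is about 7 points at 44 to 50 per arm. Cutting at 10 instead gives P(Z > 1.1) = 14% and P(Z > 0.5) = 31%, so these rates depend heavily on the cut.

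**The case against.** The best case for leaving the plan alone has four parts.

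- **An unadjusted comparison of randomised proportions is valid.** This stands. A reader might infer that, with simple randomisation and no baseline term, chance imbalance in baseline technique biases the result. The documents do not support that: randomisation makes the estimate unbiased, and the test's standard error already allows for chance imbalance.
- **This is not the leading or the sized analysis in the statistics section.** This also stands. Section 10.1 opens with improvement in the score, which uses baseline, and Section 10.2 sizes on means. A reader might infer that the sample size is undermined; it is not. The only sizing role for a proportion is one sentence in the Methods summary, which does not say which proportion it means and does not match Section 10.2. That mismatch is a separate matter.
- **Power is adequate for the stated effect.** For a 30-point difference it is already about 80% or more at 44 per arm and 86% to 95% at 50. The low-power case, 27% vs 50%, is not an effect the protocol plans for.
- **The gain depends on assumptions.** True, and at rho 0.3 it is small. A reader might take 8 points as the typical loss. That figure pairs the 30-point effect of the Methods summary with the 44 per arm of Section 10.2, a combination the protocol does not plan.

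It might also be said that adjustment belongs in a statistical analysis plan. The protocol is not silent here, however: it names the class of test, and that class cannot take a covariate.

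**Conclusion.** The point holds as a matter of efficiency on one supporting endpoint. Under the Methods summary's own design (30-point difference, 50 per arm), adjusting for baseline adds about 2 to 5 power points at rho 0.5, about 1 to 3 at rho 0.3 (0.5 in one scenario) and about 3 to 8 at rho 0.7. At rho 0.5 the gain is about 3 to 8 points with 44 per arm, about 1 to 3 with all 63 evaluable, and about 7 at 44 to 50 per arm if the true rates were 27% and 50%. All of this rests on assumed correlations, response rates, baseline spread and an underlying normal score, none of which the protocol gives. The planned test is not wrong, and neither its error rate nor the 88 is in question. This is an optional, low-cost improvement.

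**What to change.** In Section 10.1, or in the statistical analysis plan before outcome data are compared by arm, make the between-group comparison at 6 months a logistic regression of correct technique (score 10) on arm and baseline technique score, entered as a continuous covariate. Do the same at 1 and 3 months. Report the standardised (marginal) risk difference with its 95% CI, so that the result stays on the percentage-point scale of the Methods summary. Use the researcher's baseline score as the covariate, since Section 5.3 lets participants opt out of the video. Keep the crude 2x2 counts as description.

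The cost is a sentence or two of text, with no new data, visits or participants. The one drawback is that the model can fail if nearly everyone in an arm scores 10, so a fallback such as penalised likelihood should be named in advance.

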# 4 STUDY OBJECTIVES

**4.1** Primary Question/Objective:

The primary objective of the study is to answer the question: "Does use of the Clip-Tone System help people achieve and maintain effective inhaler technique for at least 6-months compared to those receiving care as usual?".

**4.2** Secondary Question/Objective:

Secondary questions that will be investigated with the data collected are:

"Do patients using the CTS have improved asthma control compared to those receiving care as usual?"

"Do patients using the CTS more frequently make fewer inhaler technique errors than those using it less frequently?"

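### The per-protocol and frequency-of-use analyses sort participants by app use after randomisation without adjusting for baseline technique, so neither isolates the device effect

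*Protocol*

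**What the plan says.** Section 10.1 of the protocol puts ITT first: "Intention to treat analysis will assess between-group differences in the patient improvement (relative to baseline) in inhaler technique score". It then adds two analyses that depend on how much the app was used.

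- **Per-protocol.** The set consists of those in the CTS arm who "used the Clip-Tone Buddy at least once per week in the first month and at least once per fortnight in thereafter". No rule is given for who counts as per-protocol in usual care. The method is one sentence: "Appropriate parametric and non-parametric tests will be used". No covariate is named.
- **Frequency of use.** "We will seek to examine any correlation between frequency of use of the Clip-Tone system in the intervention group to mean inhaler technique scores". This serves one of the two secondary questions in section 4.2: "Do patients using the CTS more frequently make fewer inhaler technique errors than those using it less frequently". Section 5.2 also lists, among its aims, learning how often the CTS should ideally be used.

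Two further statements bear on this. Section 5.2 (Methods) asks only the CTS group for screenshots of app use. Section 10.1 also plans to look at who complied: "Characteristics of participants who had higher compliance will also examined".

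**The concern.** App use is behaviour that follows randomisation. Once one arm is cut down to its sustained users, the two groups are no longer those that randomisation made comparable. Sustained users may differ from the rest in motivation, in starting technique, or in willingness to stay engaged to month 6. Usual-care participants with the same traits are not picked out, and a test of means or medians cannot separate those traits from the device.

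The frequency analysis has the same weakness inside one arm. It relates use to score levels, whereas the ITT analysis uses improvement from baseline. Starting technique can influence both how often someone uses the app and how they score later, so a correlation can arise, or be hidden, without any effect of use.

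At stake is how the two results are read: as the effect in people who use the device, and as evidence on a desirable frequency of use. Neither reading is supported by the analysis as written.

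**Working it through.** **1. The plan's own figure.** Section 10.2 gives end-of-study means of 8.9 and 9.5, SD 1 in each group, and significance level 0.05. Power and sidedness are not stated; 80% and two-sided are assumed here.

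n per arm = 2 × (1.960 + 0.842)² × 1² / 0.6² = 43.6, so 44 per arm and 88 in total. Then 88 / 0.70 = 125.7, so 126. Both stated figures reproduce; no number in the plan is wrong on this point. The planned difference is 9.5 − 8.9 = 0.6 points.

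**2. Shift from filtering one arm, with no device effect.** Let f be the fraction of the CTS arm meeting the use rule and r the correlation between a normally distributed engagement trait and the analysed outcome. If the top fraction f on that trait is kept:

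shift = r × SD × λ, with λ = φ(z) / f and z = Φ⁻¹(1 − f).

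Neither f nor r is in the protocol, so both are assumptions. SD is set to 1, as in section 10.2.

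- f = 0.6: z = −0.253, φ(z) = 0.386, λ = 0.644
- f = 0.4: z = 0.253, φ(z) = 0.386, λ = 0.966

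| f | r = 0 | r = 0.2 | r = 0.3 | r = 0.4 |
|---|---|---|---|---|
| 0.6 | 0 | 0.129 | 0.193 | 0.258 |
| 0.4 | 0 | 0.193 | 0.290 | 0.386 |

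At f = 0.6 the range is 0.129/0.6 = 21% to 0.258/0.6 = 43% of the planned difference. Over a wider grid (f from 0.4 to 0.8, r from 0.1 to 0.5) the shift runs from 0.04 to 0.48 points. A negative r gives the same sizes with the opposite sign.

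**3. Effect on the test.** Take 44f kept CTS participants against 44 in usual care. The variance in the kept group is v = 1 − r²λ(λ − z), and SE = √(v/(44f) + 1/44). At f = 0.6 and r = 0.3: v = 0.948, SE = √(0.948/26.4 + 1/44) = 0.242, and shift/SE = 0.193/0.242 = 0.80. The two-sided rejection rate is then 12.5% instead of 5%. Over the wider grid it runs from 5.3% to 45%.

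**4. What a complier-average estimate would do.** The usual remedy divides the ITT effect by the proportion complying, and assumes that non-compliers gain nothing. In section 5.2, everyone allocated to CTS is sent the device and booked a training visit, so someone below the weekly/fortnightly threshold may still benefit. Suppose 60% comply and gain 0.6, and the other 40% gain half of that:

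- ITT effect = 0.6 × 0.6 + 0.4 × 0.3 = 0.48
- complier estimate = 0.48 / 0.6 = 0.80, against a true 0.60 in compliers

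The excess of 0.20 points is of the same order as the shift in step 2. The threshold rule is therefore a poor main definition of compliance; any use of the CTS fits the assumption better.

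**The case against.** The strongest reply is that both analyses are secondary to ITT, that the frequency analysis is worded as a correlation, and that covariates for supportive analyses usually sit in the statistical analysis plan, which is not at hand. Much of this stands and limits the weight of the point. It does not remove it: the one-arm use rule is fixed in the protocol itself, and app-use data are requested only in the CTS arm, so no later document could apply the same filter to usual care.

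Three stronger readings are tempting, and the protocol does not support them.

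- *That the per-protocol result will tend to favour CTS even if the device does nothing.* The sign is unknown. People with poor technique may use a feedback app more, and proficient people may stop. The illustration applies to whichever outcome is analysed. If that is improvement from baseline, as in the ITT analysis, stable differences present at entry are subtracted out, and only engagement related to change matters. The score is also capped at 10 with planned means near 9, so a normal model is rough. Eligibility in both arms requires willingness to check technique regularly on a device (section 6.1), which may narrow differences in motivation.
- *That the protocol states a comparison with unfiltered usual care.* It names no comparator. This is the natural reading of a rule written for one arm, but it is an inference.
- *That the per-protocol result is meant to drive adoption claims.* The background section links uptake to technique scores and the health economic assessment, and does not mention the per-protocol set.

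**Conclusion.** The point holds in a limited form. As written, the per-protocol set is defined by sustained app use in one arm, with no usual-care criterion and no adjustment, and the frequency-of-use analysis ignores baseline technique. Neither can be read as an effect of the device or of using it more often. That conclusion follows from the design of the two analyses and needs no assumed number.

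The size does need assumptions. With no device effect, 60% meeting the rule, r of 0.2 to 0.4 and SD 1, the shift is about 0.13 to 0.26 points against a planned 0.6, and it is zero if engagement and the analysed outcome are unrelated. These are sensitivity values, not estimates of what this trial will show.

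The ITT analysis is unaffected. A reader might also infer that the per-protocol analysis should be replaced by a complier-average estimate using the same use threshold. That does not follow, because such an estimate has its own bias when below-threshold users benefit.

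**What to change.** In section 10.1, or in the statistical analysis plan:

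1. **Adjust for baseline technique.** For the per-protocol comparison, regress the 6-month score on arm and baseline score. For frequency of use, within the CTS arm, regress the 6-month score on frequency of use and baseline score. The baseline score is already collected from everyone.
2. **State the comparator** for the per-protocol analysis.
3. **Label both analyses** as non-randomised and supportive, and say that the conclusion rests on ITT. The label is still needed after adjustment, because baseline score does not capture motivation or other differences between users and non-users.
4. **If an effect in users is wanted, add a complier-average estimate** with randomised arm as instrument and baseline score as covariate, keeping everyone in the arm assigned. Use any CTS use as the compliance definition, with the weekly/fortnightly rule as a sensitivity analysis only. State the assumption that non-compliers gain nothing.
5. **Ask usual-care participants about CTS use** at the existing visits, where they already report the input they have had. Section 5.2 notes that the device is available on prescription and the app can be bought.

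The cost is a little more analysis, one extra question at visits already planned, and a wider interval for the complier estimate. Items 1 to 3 need no new data.
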